#### **Regimen 1) 5-Fluorouracil, Epirubicin, Cyclophosphamide (FEC 75)**

Six cycles of epirubicin, dose 75mg/m^2 per cycle, given 3 weeks apart.

#### **Regimen 2) Epirubicin, Cyclophosphamide (EC 90)**

Six cycles of epirubicin dose 90mg/m^2 per cycle, given 3 weeks apart

### **15.2. Dose Modifications and Dose Delays to chemotherapy**

Dose reductions and dose modifications for adjuvant chemotherapy will be at the discretion of the treating oncologist. These will be recorded in the CRF.

## 16. Pharmacovigilance

### 16.1. Definitions

#### 16.1.1. Adverse Events

Adverse Events (AEs) are defined as **any** new medical occurrence, or worsening of a pre-existing medical condition in a patient who has been randomised as part of the trial, which does not necessarily have to have a causal relationship to enalapril (Investigational Medicinal Product (IMP)) or trial-related procedures. Medical conditions, symptoms or diseases present at baseline will only be considered adverse events if they worsen after randomisation. Adverse events that are unequivocally due to disease progressions should not be reported as an AE during the trial.

#### 16.1.2. Adverse Reaction

Any untoward and unintended response in a patient to enalapril (IMP) which is related to any dose administered to the patient. All Adverse Events considered as having a causal relationship to the IMP will be considered an Adverse Reaction (AR).

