  - are pregnant or breastfeeding;
  - for patients of childbearing potential only: refusal to use adequate contraception throughout the trial;
  - Previous Herceptin treatment or planned Herceptin treatment within four weeks following anthracycline chemotherapy;
  - any other cancer diagnosis;
  - participation in other interventional medicinal trials in the past 6 months;
  - judgment by the Investigator that the patient should not participate in the study.

---

**Primary Objective:** To establish the effectiveness of the angiotensin-converting enzyme inhibitor (ACEI) enalapril maleate (enalapril) in preventing cardiotoxicity in patients with breast cancer undergoing adjuvant epirubicin-based chemotherapy.

---

**Primary Outcome:** The primary outcome of PROACT is the presence or absence of cardiac troponin T release at any time during epirubicin treatment, and one month after the last dose of epirubicin.

---

**Secondary Outcomes:** Secondary outcomes will focus on the effectiveness of enalapril in preventing cardiotoxicity. These include important measures of cardiac function which relate directly to patient outcomes:

- cardiac function assessed by echocardiogram, including global longitudinal strain (GLS), and measurements of left ventricular ejection fraction (LVEF), at baseline and following completion of anthracycline chemotherapy;
- cardiac troponin I release at any time during adjuvant chemotherapy and one month after the last dose of

---

---

epirubicin;

- adherence to enalapril;
- side effects of enalapril;
- adverse events;
- any anxiety or distress related to trial participation.

---

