### 8.2. Secondary Objectives

- To assess cardiac function echocardiographically, with measurements including global longitudinal strain (GLS), and left ventricular ejection fraction (LVEF), at baseline and following completion of adjuvant chemotherapy, using blinded echocardiography.
- To compare cardiac troponin I release during adjuvant chemotherapy and one month after the last dose of epirubicin;
- To quantify the level of adherence to enalapril;
- To quantify the side effects of enalapril in this patient population;
- To measure any anxiety or distress related to trial participation.

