### 9.3. Secondary Outcomes

In addition to a full description of the populations in each group throughout the trial, the following outcomes will be measured:

- cardiac function assessed by echocardiogram, including global longitudinal strain (GLS), and measurements of left ventricular ejection fraction (LVEF), at baseline and following completion of adjuvant chemotherapy;
- cardiac troponin I release during adjuvant chemotherapy and one month after the last dose of epirubicin;
- adherence to enalapril;
- adverse reactions to enalapril;
- adverse events;
- any anxiety or distress related to trial participation.
- cancer and chemotherapy outcomes in the population under study

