#### **14.5. Known side effects**

Very common side effects related to treatment with enalapril include: cough, dizziness, nausea, asthenia, blurred vision, and hyperkalaemia. Common and severe side effects include angioedema and renal impairment. More detailed information relating to the side effects of enalapril can be found in the SmPC for the product. See Appendix 1.

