### 16.1.6. Causality

The relationship of each adverse event must be determined by a medically qualified individual who is on the delegation log for the trial. If any doubt about the causality exists, the local Principal Investigator should inform the Chief Investigator. The following definitions should be used to determine causality:

Unrelated	The event is not considered to be related to enalapril.
Unlikely to be related	The event is considered unlikely to be related to enalapril; there is little evidence to suggest a causal relationship or there is another reasonable explanation for the event.
Possibly related	Although the relationship to enalapril, cannot be ruled out, the nature of the event, the underlying disease, concomitant medications or temporal relationship make other explanations plausible.
Probably related	The temporal relationship and an absence of a more likely explanation suggest that enalapril is the most likely cause.
Definitely related	The known effects of enalapril indicate this to be the most likely cause and other contributing factors can be ruled out.

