### 17.1. Statistical Analysis

Data cleaning and analysis will be provided by staff within NCTU and Durham University. Primary analysis will follow intention to treat principles with patient data analysed according to randomisation and irrespective of intervention received; other analysis groups such as per-protocol may be considered subsequently. Every effort will be made to retain and include all patients who are part of the trial.

A full statistical analysis plan (SAP) will be developed for the outcome measures and agreed with the IDMEC and Chief Investigator prior to any analysis being undertaken.

Outcome data will be analysed at the end of the study, no interim analyses is planned.

The primary analysis of presence or absence of cardiac troponin T will be assessed using Fisher's exact test. Analysis of the secondary endpoints will be dependent upon the nature of the specific endpoint and data structure; global longitudinal strain (GLS) and left ventricular ejection fraction (LVEF) will be analysed as a change from baseline using a t-test to compare intervention and control groups.

Cardiac troponin I data will also be analysed using Fisher's exact test. Changes in cardiac troponin T and I will also be analysed as a continuous variable. Additional analysis of the primary endpoint will be performed using logistic regression to account for baseline factors (regimen and HER2 status). Adverse events data will be analysed using cross-tabulation. Sensitivity analysis will also be performed for adherence to the protocol.

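### The side-effect objective rests on unblinded attribution that only the enalapril arm can receive, and section 17.1 states no between-arm estimate from the events, potassium, creatinine and blood pressure recorded in both arms

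*Combined protocol and SAP*

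**What the plan says.** The secondary objective in 8.2 is "To quantify the side effects of enalapril in this patient population". The synopsis names the matching outcome "side effects of enalapril"; section 9.3 names it "adverse reactions to enalapril". In both lists, adverse events are a separate item.

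Section 16.1.2 defines an adverse reaction as "Any untoward and unintended response in a patient to enalapril (IMP) which is related to any dose administered to the patient", and adds: "All Adverse Events considered as having a causal relationship to the IMP will be considered an Adverse Reaction (AR"). On who decides, 16.1.6 says: "The relationship of each adverse event must be determined by a medically qualified individual who is on the delegation log for the trial". The trial is open label (11.7). Blinded endpoint review covers troponin T, troponin I and the echocardiogram (19.5), not adverse events.

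The harms analysis in 17.1 Statistical Analysis is one sentence: "Adverse events data will be analysed using cross-tabulation". That section names no analysis of potassium, creatinine or blood pressure. Both arms have U&Es at baseline, before cycles 2-6 and one month after the last epirubicin dose (13.2.9), and BP at baseline, before each cycle and at completion (13.2.7).

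**The concern.** A count of attributed reactions measures two things at once: what enalapril does, and how readily a clinician who knows the allocation blames it. The second is hard to control here. Section 14.5 lists the very common enalapril effects as "cough, dizziness, nausea, asthenia, blurred vision, and hyperkalaemia". Nausea is also among the foreseeable events of routine care in 16.2, and asthenia is hard to tell from the fatigue listed there. Section 16.1.6 has five causality categories, including one for a possible relation in which other explanations remain plausible, and the protocol does not say which categories make an event a reaction.

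The control arm supplies the background rate that attribution has to guess, but the plan does not say that this rate will be used for the side-effect objective. According to 7.5, the results are to inform whether enalapril is given routinely. That decision needs a credible estimate of harm beside the troponin result.

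**Working it through.** **The plan's own figure.** The only sample size is for troponin T: 47% against 20%, two-sided alpha 5%, power 90%. The normal approximation gives [1.96 x sqrt(2 x 0.335 x 0.665) + 1.2816 x sqrt(0.47 x 0.53 + 0.20 x 0.80)]^2 / 0.27^2 = 62.1, so 63 per arm, or 70 per arm with a continuity correction. That reproduces the stated 140. Full enumeration of Fisher's exact test at 70 per arm gives 90.8% power. This point does not affect that figure. The protocol states no rate or precision for side effects, so the rates below are assumptions.

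**What an attributed count can show.** Let b be the background incidence, x the true excess due to enalapril, and f and s the shares of background and excess events that are attributed. The enalapril-arm reaction rate is b x f + x x s. The control rate is 0 by construction, and the true risk difference is x.

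| b | x | f | s | Reaction rate | True difference |
|---|---|---|---|---|---|
| 50% | 0 | 0 / 20% / 50% | - | 0 / 10% / 25% | 0 |
| 30% | 0 | 20% / 50% | - | 6% / 15% | 0 |
| 30% | 10% | 0 | 50% | 5% | 10% |
| 30% | 10% | 50% | 100% | 0.30 x 0.5 + 0.10 = 25% | 10% |

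The error can go either way. If someone tested the count between arms, 6 of 85 against 0 of 85 would already give Fisher p = 0.029, whatever the drug does.

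**What the randomised comparison would give.** The 95% half-width at equal rates is 1.96 x sqrt(2p(1-p)/n). The detectable increase is at 80% power.

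| Assumed incidence p | Half-width, 85 per arm | Half-width, 70 per arm | Detectable increase, 85 (70) per arm |
|---|---|---|---|
| 10% | 9.0 points | 9.9 points | 16.5 (18.6) points |
| 30% | 13.8 points | 15.2 points | 21.0 (23.2) points |
| 50% | 15.0 points | 16.6 points | 20.9 (22.9) points |

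For a mean difference in potassium, creatinine or systolic BP, before any gain from baseline adjustment, the half-width is 1.96 x sqrt(2/n) = 0.30 SD at 85 per arm and 0.33 SD at 70.

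**Where the arms are comparable.**

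- Common on-drug points are five for U&Es (before cycles 2-6) and six for BP (before cycles 1-6).
- Enalapril stops three weeks after the last epirubicin dose (14.6.6) and the completion visit is at four weeks (13.1, note g), so completion values are taken about 4 - 3 = 1 week off drug.
- Up to three dose evaluation visits, with BP, U&Es and a side-effect check, belong to the enalapril arm only (13.2.7, 13.2.9, 14.6.2 to 14.6.4). Events are asked about at every visit (16.5), so a crude all-visit comparison would find more events in that arm.
- Section 14.6.2 withdraws patients with specified creatinine, potassium or BP findings at dose evaluation visit 1, before the common U&E points. AE recording ends at withdrawal except for events judged related to enalapril (16.5). Later means would therefore omit the patients most affected.

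**The case against.** The strongest reply is that the data are already collected and partly planned for. Adverse events are a separate secondary outcome (synopsis, 9.3), defined regardless of causality in every randomised patient (16.1.1), recorded from randomisation (16.5) and cross-tabulated (17.1). This stands. A reader might infer that the plan replaced a randomised comparison with an attributed count, and the documents do not support that. A comparison by arm is possible and perhaps intended; it is only unspecified and not tied to the side-effect objective.

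A reader might also infer that reactions will be tested between arms against a structural zero. No such test is planned. Section 8.2 uses the verb compare for troponin I and quantify for side effects, so a descriptive reading is fair. Nor is 16.1.2 itself at fault: it is a pharmacovigilance definition, and the weakness is its use as the outcome in 9.3 with no estimator in 17.1.

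The full SAP that 17.1 promises is not among the documents and may supply the detail, so its absence is not a decision against it.

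Finally, the randomised comparison is not free of bias. Symptom reporting stays open label, ascertainment differs between arms, and early withdrawal is selective. These limits shape the fix but do not rescue attribution, which shares the first of them and adds an unblinded causal judgement.

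**Conclusion.** The point holds in a limited form. As written, the side-effect objective is answered by a count that depends on unblinded attribution and can arise in one arm only. The plan states no between-arm estimate of harm and no use of potassium, creatinine or BP. Under the assumed inputs, the attributed rate ranges from 0% to 25% when the true excess is zero, and from 5% to 25% when it is 10 points. These ranges follow from assumed background rates and attribution shares and are not forecasts. The randomised difference would be imprecise (about 9 to 17 points either side over assumed incidences of 10% to 50%) but would not depend on attribution. The primary outcome, sample size and main conclusion are unaffected. The change should be made because it concerns a stated objective and uses data already collected.

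**What to change.** In 9.3 and the SAP, answer the side-effect objective as follows.

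1. Give the all-cause incidence of a fixed list of known enalapril effects (cough, dizziness, nausea, asthenia, blurred vision, hypotension, hyperkalaemia, renal impairment, angioedema) by randomised arm, with risk difference and 95% CI.
2. Compare potassium and creatinine before cycles 2-6, and systolic BP before cycles 1-6, between arms with adjustment for baseline. Show the completion visit separately.
3. Report events and values found only at dose evaluation visits in their own table. Count patients withdrawn at those visits as having had the event, so that later comparisons do not understate harm. Because control patients are not examined then, show the difference with and without these cases.
4. Keep attributed reactions as a descriptive table for the enalapril arm only, stating which causality categories count.

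The cost is SAP wording and a few tables, with no new data and no change to the 170. The intervals are wider than for a one-arm percentage: at the same rate and n, the variance is 2p(1-p)/n instead of p(1-p)/n, so they are sqrt(2) = 1.41 times as wide. Symptom reports remain open label.

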#### 16.1.3. Unexpected Adverse Reaction:

Any Adverse Reaction, the nature and severity of which is not consistent with the information about enalapril maleate in the SmPC.

#### 16.1.4. Serious Adverse Events (SAE) or Serious Adverse Reaction (SAR)

Any untoward or unexpected medical occurrence (Adverse Event, Adverse Reaction, or Unexpected Adverse Reaction) that:

- Results in death,
- Is life-threatening\*,
- Requires hospitalisation or prolongation of existing hospitalisation,
- Results in persistent or significant disability or incapacity,
- Is a congenital anomaly or birth defect,
- Any other important medical condition which, although not included in the above, may require medical or surgical intervention to prevent one of the outcomes listed.

\* life-threatening refers to an event in which the patient was at risk of death at the time of the event; it does not refer to an event which hypothetically might have caused death if it were more severe.

#### 16.1.5. Suspected, Unexpected Serious Adverse Reaction (SUSAR)

A serious adverse reaction, the nature and severity of which is not consistent with the information about the IMP in question set out in the RSI.

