## 16.2. Foreseeable Adverse Events

Foreseeable adverse events are those which are foreseen in the patient population and as a result of the routine care of patients. If a foreseeable adverse event occurs, and this also fulfils the criteria for an SAE it will not need an SAE report to be submitted for this trial, but will need recording on the CRF as an adverse event. These will not be considered as SUSARs unless the severity of the event was considered to be unexpected.

Foreseeable adverse events are:

- Infection
- Anaemia
- Thrombocytopenia
- Neutropenia
- Nausea
- Vomiting
- Fatigue
- Alopecia
- Diarrhoea
- Stomatitis
- Loss of appetite
- Palmar-plantar syndrome
- Taste changes
- Bladder irritation
- Headache
- Skin changes
- Thrombosis
- Sepsis
- Neutropenic sepsis

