## 16.5. Adverse Event Reporting

All AEs will be recorded in the patients' medical notes and on electronic case report forms. AEs will be recorded from the day of randomisation until the last visit or until withdrawal, with the exception of adverse events considered related to enalapril, which will be followed until resolution, a stable outcome or death.

All AEs will be assessed for severity, causality, and seriousness and expectedness by an Investigator. All events will be reviewed by the Independent Data Monitoring and Ethics Committee (IDMEC) as part of their ongoing assessment of safety.

Patients should be asked about any adverse events at each visit.

Where an AE fulfils the criteria for a reportable SAE as part of this trial, this will be reported immediately to NCTU (within 24 hours of the research team becoming aware of the event) who will inform the Sponsor and Chief Investigator. Should the SAE form be incomplete at the time of the initial report, follow-up information should be provided as it becomes available. The relationship to the IMP should be assessed by the Investigator at the site, and they will also assess expectedness in relation to the approved RSI.

Exceptions for SAE reporting include hospitalisation for:

- Routine treatment or monitoring of the studied indication not associated with any deterioration in condition
- Treatment which was elective or pre-planned, for a pre-existing condition not associated with any deterioration in condition
- Any admission to hospital or other institution for general care where there was no deterioration in condition

In the event that a SUSAR is fatal or life-threatening, the sponsor will inform the MHRA and the REC within 7 days. In the event that a SUSAR is non-life-threatening, the sponsor will inform the MHRA and the REC within 15 days.

All Principal Investigators will be informed of all SUSARs throughout the trial, as they occur.

SAEs and SUSARs should be reported to NCTU within 24 hours

[[contact]](mailto:[contact])

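### The SUSAR definition (16.1.3, 16.1.5) can be read as needing both nature and severity to be inconsistent, so an enalapril reaction of listed nature but unlisted severity could miss expedited reporting

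*Combined protocol and SAP*

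**What the plan says.** All references are to the combined protocol and SAP.

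- **16.1.3** treats an adverse reaction as unexpected when it is one "the nature and severity of which is not consistent with the information about enalapril maleate in the SmPC".
- **16.1.5** makes a serious reaction a SUSAR on this test: "the nature and severity of which is not consistent with the information about the IMP in question set out in the RSI".
- **16.2** lists foreseeable events and sets their scope: "Foreseeable adverse events are those which are foreseen in the patient population and as a result of the routine care of patients". It exempts them from SAE reports and adds: "These will not be considered as SUSARs unless the severity of the event was considered to be unexpected". Nausea is on the list. Hyperkalaemia, angioedema and renal impairment are not.
- **14.5** names cough, dizziness, nausea, asthenia, blurred vision and hyperkalaemia as very common with enalapril, and continues: "Common and severe side effects include angioedema and renal impairment".
- **16.5** gives the judgement to the site investigator: "they will also assess expectedness in relation to the approved RSI". It then sets the clocks: "In the event that a SUSAR is fatal or life-threatening, the sponsor will inform the MHRA and the REC within 7 days", with 15 days for a SUSAR that is not life-threatening. All Principal Investigators are told of every SUSAR.

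**The concern.** SUSAR status is the only trigger in 16.5 for the 7- and 15-day reports and for notice to the other sites. The definition behind it should therefore give one answer for any given event. Joined by *and*, the two conditions can be taken as both necessary. A serious reaction already known for enalapril would then count as expected however far its severity went beyond the reference information.

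No other section says how to class that case. Section 16.5 sends the investigator to the RSI but does not say whether a mismatch in severity alone is enough, and it describes no second assessment of expectedness by the sponsor or NCTU. Four Trusts recruit (9.4), so several investigators will apply the wording separately.

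**Working it through.** No arithmetic applies, because the point concerns the logic of the definitions. Take a serious adverse event judged related to enalapril. Let N mean that its nature is inconsistent with the RSI, and S that its severity is inconsistent with the RSI.

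**Two readings of 16.1.5**

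- Reading A (both must fail): SUSAR if N and S.
- Reading B (nature and severity form one profile, which fails if either part fails): SUSAR if N or S.

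| N | S | Reading A | Reading B |
|---|---|---|---|
| no | no | not a SUSAR | not a SUSAR |
| yes | yes | SUSAR | SUSAR |
| no | yes | not a SUSAR | SUSAR |
| yes | no | not a SUSAR | SUSAR |

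The readings part in the last two rows. The third row matters in practice: a known kind of reaction, more severe than listed.

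**Setting 16.2 beside it.** For events on the foreseeable list, 16.2 rules out SUSAR status unless severity is unexpected. The event must still be serious and related to enalapril, so S is necessary there but not sufficient. The clause shows that the authors saw severity as able to decide the matter.

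**Hyperkalaemia: the gap.** It is named in 14.5 and absent from the 16.2 list, so only 16.1.5 governs it. Suppose its nature is in the RSI and a serious case goes beyond the severity described there (N no, S yes). Reading A gives no SUSAR, hence no 7- or 15-day report and no notice to Principal Investigators. Reading B gives all of these.

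**Nausea: the collision.** It is in 14.5 and on the 16.2 list. Suppose a serious, related case with its nature in the RSI and unexpected severity (again N no, S yes). Reading A of 16.1.5 says it cannot be a SUSAR. Section 16.2 leaves that open, precisely because the severity is unexpected. Under Reading A the exception in 16.2 could never operate for nausea.

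**What still works without SUSAR status.** A reportable SAE goes to NCTU within 24 hours, and NCTU informs the sponsor and Chief Investigator (16.5). Deaths judged to be caused by enalapril go to the sponsor immediately (16.7). Urgent safety measures are notified to the MHRA and REC within 3 days (16.8). The IDMEC reviews all events (16.5) and meets every six months (20.6). These routes cover hyperkalaemia reasonably well. For nausea the first is missing, since 16.2 and 16.6 exempt listed events from SAE reports.

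**The reference document.** Section 16.1.3 judges against the SmPC; 16.1.5 and 16.5 judge against the RSI. No reporting step hangs on 16.1.3 alone, so this mismatch has no shown effect on reporting.

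**The case against.** The strongest reply is that the text never says that both features must be inconsistent. The singular verb fits a reading in which nature and severity form one profile, and a mismatch in either part makes the reaction unexpected. Section 16.2 points the same way. This stands: a reader might infer that the protocol expressly demands both, and the documents do not support that. What they support is that the wording allows two readings with opposite results.

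A reader might also infer that two investigators could class the same fatal angioedema in opposite ways, one under 16.1.5 and one under 16.2. That does not follow. Neither angioedema nor renal impairment is on the 16.2 list, so nobody following the protocol would apply 16.2 to them. Section 14.5 already describes both as severe, and whether a fatal form would exceed the RSI cannot be judged from the text supplied.

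Nor do chemotherapy-type events get a more protective test overall. Section 16.2 states a condition inside an exemption and is not a second SUSAR definition. The listed events are spared SAE reports even when they meet the SAE criteria, whereas a serious enalapril reaction off the list must be reported within 24 hours.

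The existing safeguards also stand, and they limit the harm. They do not replace an expedited report to the MHRA and REC or notice to the other sites.

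**Conclusion.** The point holds as an ambiguity in an operative safety definition. One natural reading of 16.1.3 and 16.1.5 classes a serious enalapril reaction of listed nature but unlisted severity as expected. No other section settles the question, and that reading conflicts with 16.2 for nausea.

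What is at stake is a missed 7- or 15-day report and missed notice to Principal Investigators. For SAEs off the 16.2 list, the sponsor and Chief Investigator would still be told. The documents give no rate for such reactions, so no count can be calculated; among the 85 patients allocated enalapril it is likely to be small. Sample size, alpha and the primary analysis are unaffected.

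The conclusion assumes that the RSI lists nausea and hyperkalaemia, as 14.5 suggests, and that a case could exceed the severity described there. The RSI is not in the text supplied, so neither assumption could be confirmed.

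**What to change.** In 16.1.3 and 16.1.5, replace *nature and severity* with *nature or severity*, so that an inconsistency in either makes the reaction unexpected. This agrees with the role that 16.2 gives to severity. It also gives investigators at all sites one rule for the case that 16.5 leaves open.

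As tidying only, name the approved RSI in 16.1.3 in place of the SmPC, so that 16.1.3, 16.1.5 and 16.5 use one reference.

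The cost is a few words in two definitions and possibly a few more expedited reports. No visit, endpoint, treatment rule or analysis changes.
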